# **Study Protocol**

#### **List of Abbreviations:**

ANOVA – Analysis of variance EEG - Electroencephalogram

DLPFC – Dorsolateral prefrontal cortex

DSM-5 – Diagnostic Statistical Manual version 5

FTND – Fagerstrom Test for Nicotine Dependence

MNWS – Minnesota Nicotine Withdrawal Scale

tDCS – Transcranial direct current stimulation

### 1.1: Title

The Effects of Transcranial Direct Current Stimulation on EEG changes in Nicotine use disorder patients: An Exploratory Study

#### 1.7: Conflict of interest

Please refer to the Conflict-of-Interest form.

## 2.1: Literature Reviews

Cigarette smoking is recognized as the leading preventable cause of death worldwide, surpassing other factors [5]. The smoke produced by cigarettes, originating from the heating or combustion of tobacco leaves, contains a blend of chemicals that are known for their oncogenic, teratogenic, cytotoxic, and mutagenic properties [6]. Globally in 2019, smoking tobacco use accounted for 7.69 million (7.16–8.20) deaths and 200 million (185–214) disability-adjusted life-years and was the leading risk factor for death among males (20.2% [19.3–21.1] of male deaths). 6.68 million [86.9%] of 7.69 million deaths attributable to smoking tobacco use were among current smokers.[7]. Despite these well-documented risks nearly half of the male population in Malaysia, are engaged in smoking. Furthermore, in Malaysia alone, smoking-related diseases are responsible for the deaths of up to 27000 individuals each year [8]. In 2023, Malaysia spent an estimated RM16 billion annually on treating smoking-related illnesses such as cardiovascular disease and lung cancer [8, 9].

The harmful health effects observed are likely due to nicotine addiction, a condition marked by an inability to resist compulsive drug-seeking behavior despite negative consequences [10, 11]. Neuroimaging studies have shown that the dorsolateral prefrontal cortex (DLPFC) plays a vital role in controlling the urge and reward sensations associated with smoking [2]. This suggests its involvement in maintaining abstinence and managing cue-induced cravings [2]. In smoking cessation research, the main areas of focus are craving, drug-seeking behavior, expectation-related aspects, and relapse. Although targeting smoking cue reactivity through brain stimulation has proven effective, cravings during abstinence have been found to be more reliable predictors of relapse than those induced by external cues [12]

Transcranial direct current stimulation (tDCS) is a non-invasive, painless brain stimulation method that uses direct electrical currents to target specific brain regions [13]. This technique involves applying a low-intensity current (1-2 mA) to the scalp using anodal and cathodal electrodes. Anodal polarization results in depolarization of the resting membrane potential, increasing neural excitability, while cathodal polarization leads to hyperpolarization, decreasing neural activity [13]. The type and duration of these changes in neural excitability depend on factors such as the polarity, intensity, and duration of the stimulus. The lasting effects of the stimulus depend on the duration of its application [13]. Recent research by Mangia et al. has provided valuable insights into the immediate neurophysiological changes induced by tDCS[14]. In their study, EEG activity was measured in ten healthy subjects during and after a session of anodal stimulation of the postero-parietal cortex. This approach was aimed at detecting tDCS-induced alterations in brain activity. The study revealed several key findings: firstly, there was an increase in theta band activity observed during the initial minutes of stimulation. Secondly, enhancements in alpha and beta power were noted both during and after the stimulation period. Lastly, the study reported a widespread activation across several brain regions [14].

Smoking addiction involves multiple brain regions, including the insula, ventral tegmental area, prefrontal cortex, and hippocampus. Altering the activity in these areas by applying anodal tDCS has been shown to influence smoking behavior [13]. Applying anodal tDCS to the DLPFC, which causes neuronal depolarization, reduces cravings in

response to smoking cues. This discovery that non-invasive stimulation can alter cue-induced cravings provides significant insights into the mechanisms of addiction and relapse. Another study by Verveer, Remmerswaal [15] showed that these immediate EEG changes suggest a complex pattern of neural modulation, which could underlie the observed long-term benefits in cognitive functions such as selective attention and motor inhibition.

The primary goal of this study is to assess whether transcranial direct current stimulation, a powerful form of non-invasive brain stimulation, can focus on the dorsolateral prefrontal cortex (DLPFC), a critical region involved in cognitive control over smoking cravings and behaviors. The study uses Electroencephalography (EEG) to track changes in brain activity, aiming to understand the effects of tDCS on brain functions in individuals with nicotine dependence.

# 2.2: Risk and benefit to study participants

## **Potential adverse events:**

- 1. Itching (39.3%) [3]
- 2. Tingling sensation in the first few seconds of tDCS stimulation (22.2%) [3]
- 3. Headache (14.8%) [3]
- 4. Burning sensation (8.7%) [3]
- 5. Retinal phosphenes [4]
- 6. Nausea and insomnia (2.9%) [4]
- 7. Brainstem stimulation (extremely rare one case reported) [2]
- 8. Seizure (extremely rare one case reported) [3]
- 9. Electrochemically produced toxic brain products (unlikely as electrodes not in direct contact with brain tissue) [2]
- 10. Metallic electrode dissolution products caused by electrode-tissue interface (unlikely as electrodes not in direct contact with brain tissue) [2]
- 11. Skin damage at the interface due to heat production (unlikely with the protocol used) [2]
- 12. Neuronal hyperactivity and tissue heating (protocol induce moderate cortical excitability as 50% of total charge enters brain which causes subthreshold production of action potential, damage from heat could be ruled out) [2]

#### Safety criteria

- 1. Non-metallic, conductive rubber electrodes soaked in saline are used to potential adverse events 9, 10 and 11 [2]
- 2. Current density below 25mA/cm^2 does not cause tissue damage even at higher frequency over a few hours (study would use 2mA with current density of 0.03-0.08 mA/cm^2 for 20 minutes per session) [2]
- 3. Current protocol would not cause heating effect and would not increase serum neuron-specific enlase (marker for neuronal damage) [1,2]. Protocol would not cause changes in diffusion-weighted or contrast enhanced MRI [2]
- 4. This method would also not produce permanent or structural cortical changes [2]
- 5. Ramping up current to prevent retinal phosphenes [4]
- 6. Device giving out current density that does not fluctuate [2]. This study hopes to reduce the number of cigarettes smoked from baseline and thus propelling tDCS to constitute a treatment modality for nicotine addiction.

## 2.2.1: Justification acceptable risk

As stated in the literature above, there are no serious side effects known to be caused by tDCS. The study procedure follows methodology that has been outlined by other safety, ethical, legal regulatory and application guideline papers.

The potential adverse events are listed in order of rarity and safety criteria to minimize or prevent these effects.

## 3.1: Study value and outcome

This research explores the use of transcranial Direct Current Stimulation (tDCS) in treating nicotine addiction, with a focus on changes in Electroencephalogram (EEG) patterns. The study aims to assess tDCS's effectiveness as a treatment and anticipates publishing the findings in leading biomedical engineering and clinical psychiatry journals.

The research also considers the broader implications of tDCS in addiction treatment, offering innovative strategies and exploring future therapeutic interventions. A significant outcome will be a comprehensive thesis by a Ph.D. student, contributing significantly to existing knowledge.

The study serves as a foundation for larger-scale investigations, potentially extending into a pilot study and seeking substantial funding like the Fundamental Research Grant Scheme (FRGS). This approach aims to broaden the research's scope and impact, translating scientific discoveries into practical applications. The study's comprehensive nature reflects a strategic approach towards advancing understanding and treatment of nicotine addiction.

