## 3.2: Study objectives

- 1) To investigate the EEG changes (alpha, beta delta and theta wave at different region, includes prefrontal lateral lobe) before and after tDCS in nicotine use disorder subjects.
- 2) To explore the efficacy of tDCS in the treatment of nicotine withdrawal.

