#### **Data Analysis:**

will be conducted using SPSS version 29, employing a combination of Analysis of Variance (ANOVA) and paired t-tests, along with two-way repeated measures of covariates. ANOVA will be utilized to assess the overall impact of the tDCS

intervention across three time points—baseline, after one week of intervention, and six weeks post-intervention. Paired t-tests will further analyze changes from baseline at each subsequent time point. A critical aspect of the analysis will be the focus on changes in alpha, beta, delta, and theta brain waves, nicotine dependence and withdrawal symptoms, measured by the Fagerstrom Test for Nicotine Dependence (FTND) and the Minnesota Nicotine Withdrawal Scale (MNWS). The criterion for statistical significance is set at p < 0.05 for all tests to ensure the reliability and validity of the findings.

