# 5.5: Intervention group distribution

There is no specific distribution group as it's an exploratory study in which only one group is involved.

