# 5.7: Sequence of participation duration

2 weeks of active tDCS intervention (20 minutes per session, 5 days a week for consequent 2 weeks). Then in week 6th subjects need to come back for EEG recording.

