#### 11.0: Privacy and confidentiality

Subject's names will be kept on a password-protected database and will be linked only with a study identification number for this research. The identification number instead of patient identifiers will be used on subject data sheets. Single-blinded procedure will be implemented, the blinding procedure involves the identification of each subject blind from the data analyzers. All data will be entered into a computer and Google Drive that is password protected. On completion of the study, data in the computer will be copied to Google Drive that is password protected and the data in the computer erased. Hardcopy data will be stored in a locked office of the investigators and maintained for

a minimum of three years after the completion of study. The data would be destroyed after that period of storage. Participants will not be able to view their personal study data, as the data will be consolidated into a database. The subject can write to the investigators to request access to study findings but not the data collected.

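### The one-group design measures change from baseline, but the protocol sets an effectiveness aim, reads time change as the impact of tDCS, and calls de-identification single-blinding

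*Protocol*

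**What the plan says.** Three places in the protocol use the language of treatment effect:

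- Section 3.1: "The study aims to assess tDCS's effectiveness as a treatment". The sentence carries no qualification.
- Section 3.2, objective 2: "To explore the efficacy of tDCS in the treatment of nicotine withdrawal".
- Section 5.2, Data Analysis: "ANOVA will be utilized to assess the overall impact of the tDCS" intervention over T0, T1 and T6. It then adds: "Paired t-tests will further analyze changes from baseline at each subsequent time point". The significance criterion is p < 0.05 for every test.

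Two places fix the design:

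- Section 5.5: "it's an exploratory study in which only one group is involved".
- Section 5.7: "2 weeks of active tDCS intervention (20 minutes per session, 5 days a week for consequent 2 weeks". No sham, control or randomisation is described anywhere.

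On blinding, section 11.0, which deals with privacy and confidentiality, says: "Single-blinded procedure will be implemented, the blinding procedure involves the identification of each subject blind from the data analyzers".

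The enrolment target is 10 (section 6.2), given without an effect size, standard deviation or power.

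**The concern.** The claim and the design do not match. Each subject receives active stimulation and is compared only with their own baseline. The planned tests therefore estimate how EEG power, FTND and MNWS differ between visits. Calling that difference the impact of the intervention is a causal statement, and nothing in the design supplies the comparison it needs. FTND and MNWS score dependence and withdrawal symptoms, so they are open to expectation, repeated administration and changes in smoking, whether or not the stimulation works.

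The blinding statement adds to the problem. A reader, or an ethics committee, may take single-blinded to mean protection against bias in the outcomes. What section 11.0 defines is the withholding of subject identity from the analysts. With one active group there is no allocation to mask. In a before-after comparison the information that could influence judgement is which visit a record comes from, and the definition does not cover it.

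At stake is what the study may conclude. Section 3.1 looks ahead to journal publication, larger studies and grant funding, so an effect claim that the design cannot support could be carried forward.

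**Working it through.** **1. Setting the sections side by side.**

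| Element | Protocol | What it supports |
|---|---|---|
| Aim (3.1) | Effectiveness as a treatment | Needs a comparison with what would have happened without tDCS |
| Objective 2 (3.2) | Explore efficacy in withdrawal | The same, in softer wording |
| Groups (5.5, 5.7) | One group, active tDCS | Only a comparison with own baseline |
| Analysis (5.2) | ANOVA over T0, T1, T6; paired t-tests | Tests of no mean change over time |
| Blinding (11.0) | Identity hidden from analysts | Confidentiality |

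Write the mean change from baseline as

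change = tDCS effect + non-specific change,

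where the second term collects expectation, repeat testing, natural course and regression to the mean. The paired t-test and the ANOVA test whether the sum is zero. One group gives one estimate of the sum and none of its parts. Hence p < 0.05 controls the error rate for the hypothesis of no change, not for the hypothesis of no tDCS effect.

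**2. Blinding.** The factor in the analysis is visit, with levels T0, T1 and T6. The quantity hidden in section 11.0 is subject identity. These are different things, so the stated procedure, as defined, does not mask the contrast being tested.

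**3. Illustration of size.** The protocol offers no figure to reproduce: the sample size of 10 comes without inputs. The following therefore rests on assumptions.

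- From the protocol: n = 10, alpha = 0.05.
- Assumed: two-sided test (sidedness is not stated); true tDCS effect of zero; a non-specific mean shift of d, in units of the SD of the change.
- Formula: the paired t statistic follows a noncentral t distribution with 9 degrees of freedom and noncentrality d × √10. The test rejects when |t| exceeds 2.262.

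| d | noncentrality | P(p < 0.05) |
|---|---|---|
| 0 | 0 | 0.050 |
| 0.2 | 0.632 | 0.088 |
| 0.3 | 0.949 | 0.136 |
| 0.5 | 1.581 | 0.293 |

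These figures are for a single test. They show how the error rate responds to a non-specific shift; they do not estimate the shift in this study, on which the documents give no information.

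**The case against.** The strongest reply is that the study presents itself as exploratory, in its title and in sections 5.2, 5.5 and 6.2, and describes itself in 3.1 as groundwork for larger investigations. One group is a legitimate choice at that stage. Objective 1 is already worded as change before and after stimulation, objective 2 says explore, and the paired t-tests are described as changes from baseline. The blinding sentence says exactly what is hidden from whom, and no design or analysis section relies on it.

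Much of this stands. The single group is not the fault, and no second arm is being asked for. But the aim in 3.1 has no exploratory qualifier, the Data Analysis paragraph attributes the time effect to the intervention, and the blinding label remains a misnomer.

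Four stronger readings are tempting but not supported:

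- *EEG handlers will see the visit label.* The protocol does not describe artefact rejection, who performs it or how files are labelled. Silence does not show that visit is visible, and such detail may sit in an SAP that is not at hand. That part is conditional.
- *Regression to the mean of a known size will occur.* Section 6.3 requires a DSM-5 diagnosis, an age range and good health, with no symptom or dependence threshold. There is no documented selection on high scores from which to derive a magnitude, and likewise no basis for a figure on drift in EEG reading.
- *A significant result will be reported as efficacy.* The protocol has no success rule and makes no such reporting commitment. It sets the aim in those terms, which is enough for the wording to need correction.
- *The protocol declares the study open-label.* It does not use the term. That subjects know they receive active treatment is an inference from sections 5.5 and 5.7.

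**Conclusion.** The point holds as a mismatch between stated aims and design. Sections 3.1, 3.2 and 5.2 claim or imply a treatment effect that a single active group cannot identify, and section 11.0 gives the name of blinding to de-identification. The exploratory label softens this without removing it. The conclusion follows from the text and depends on no calculation.

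The possible consequence is a p < 0.05 of about 9% to 29% per test when tDCS has no effect, if the non-specific shift is 0.2 to 0.5 SD of change; with no such shift it is 5%. Those inputs are assumed. Whether unmasked visit could bias the EEG results depends on processing arrangements that the protocol does not state.

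This should be corrected before results are analysed. It does not call the one-group design into question.

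**What to change.** 1. In section 3.1, objective 2 of section 3.2 and the Data Analysis paragraph of section 5.2, restate the aim and the inference as within-subject change from baseline, reported with a 95% CI. Add a sentence that no conclusion on efficacy or effectiveness will be drawn without a concurrent comparator.
2. In section 11.0, either replace the single-blinded label with de-identified analysis, or make it real masking: have an existing team member code the EEG files so that subject and visit are both hidden until artefact rejection and band-power extraction are locked. If visit is already hidden during EEG processing, say so in the protocol.

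The cost is a few wording changes, a more modest claim and, for the masking option, a small file-coding step. No additional subjects or visits are needed and the intervention is untouched.

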## 3.2: Study objectives

- 1) To investigate the EEG changes (alpha, beta delta and theta wave at different region, includes prefrontal lateral lobe) before and after tDCS in nicotine use disorder subjects.
- 2) To explore the efficacy of tDCS in the treatment of nicotine withdrawal.

## 4.1: Ethical issue

The research will adhere to ethical principles as outlined in the Declaration of Helsinki and Malaysian Good Clinical Practice Guidelines. In addition to obtaining approval

from the National Medical Research Register (NMRR), the study will also seek approval from the Monash University Human Research Ethics Committee (MUHREC).

#### 5.1: Study endpoint

Completed the steps as indicated in the research protocol.

## 5.2: Study design

### **Study Design**

This exploratory research is focused on examining the impact of transcranial Direct Current Stimulation (tDCS) on subjects diagnosed with nicotine use disorder. The study primarily utilizes Electroencephalography (EEG) to monitor and analyze changes in cortical activities resulting from the tDCS intervention. The objective is to understand how tDCS influences brain function in individuals affected by nicotine dependence.

## **Participant Selection and Recruitment:**

For this exploratory study, participant recruitment will be carried out through various social media platforms. The eligibility criteria for participation include a confirmed diagnosis of nicotine use disorder, as defined by the DSM-5 criteria. Additionally, candidates should generally be in good health. While details such as age and gender will be recorded for each participant, they will not serve as exclusionary factors for the study. Given the exploratory nature of this research, the recruitment will be limited to a total of ten subjects.

#### **Intervention:**

Transcranial Direct Current Stimulation (tDCS) Participants will receive tDCS intervention lasting 20 minutes per session. These sessions will occur 5 days a week, spanning two weeks. The tDCS will be delivered following standardized protocols to ensure safety and uniformity across treatments.

#### **Electroencephalography (EEG) Assessments:**

EEG recordings will be conducted at three key time points: initially at baseline (T0), then after one week of the intervention (T1), and finally, six weeks following the conclusion of the intervention (T6). These EEG assessments will focus on tracking changes in alpha, beta, delta, and theta brain waves across different regions, with a specific emphasis on the Dorsolateral prefrontal cortex. This targeted approach is designed to effectively evaluate the impact of the tDCS intervention on brain activity.

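### No EEG, FTND or MNWS is scheduled at or soon after the end of the two-week course: T1 as worded is mid-course, and the only reading after all 10 sessions is T6, weeks later

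*Protocol*

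**What the plan says.** **Course.** Protocol section 5.2, Intervention: "Participants will receive tDCS intervention lasting 20 minutes per session" and "These sessions will occur 5 days a week, spanning two weeks". Section 5.7 agrees: "2 weeks of active tDCS intervention (20 minutes per session, 5 days a week for consequent 2 weeks".

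**Assessments.** Section 5.2, Electroencephalography (EEG) Assessments: "EEG recordings will be conducted at three key time points". These are baseline (T0), "then after one week of the intervention (T1", and "six weeks following the conclusion of the intervention (T6". The next paragraph of section 5.2 puts FTND and MNWS at the same three points. After the last session only a safety assessment is due (section 9.1).

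**Analysis.** Section 5.2, Data Analysis, runs the ANOVA over "baseline, after one week of intervention, and six weeks post-intervention" and compares each later point with baseline by paired t-test.

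**Objectives.** Section 3.2 asks for EEG changes "before and after tDCS in nicotine use disorder subjects" and for the efficacy of tDCS in nicotine withdrawal.

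**T6 elsewhere.** Section 5.6 gives total participation as 6 weeks, and section 5.7 places the return EEG in week 6. Neither fits a T6 that falls six weeks after the course has ended.

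**The concern.** The first objective is a before-and-after contrast around the treatment. The treatment is a two-week course, yet neither post-baseline reading is taken when that course has just been completed. One is too early to reflect all of it. The other is late enough for any effect to have faded or for something else to have changed.

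What is at stake is interpretation. Suppose EEG power or MNWS changes at T1 and is back at baseline at T6. That pattern fits a full-course effect that wore off, and it fits equally well a second week that contributed nothing. Suppose instead that both contrasts are null. An effect that was present at the end of week two and then decayed would have gone unseen. There is no control group (section 5.5) to help separate decay from drift. Each subject has one course, so a recording not made at its end cannot be replaced by a choice of analysis.

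**Working it through.** The protocol gives no effect size, SD, correlation or power figure, so there is no figure of its own to reproduce. The main check is the timeline.

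**1. Dose received at each assessment** (section 5.2, Intervention; section 5.7)
- Full course: 5 sessions per week × 2 weeks = 10 sessions; 10 × 20 min = 200 min.
- At T1, after one week: 5 × 1 = 5 sessions; 5 × 20 = 100 min. 100/200 = 50% of the course.
- At T6: all 10 sessions.

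**2. Delay from the last session to T6**
- By section 5.2 (EEG Assessments and Data Analysis): 6 weeks after the course ends, so about week 2 + 6 = 8 from the start.
- By sections 5.6 and 5.7: week 6 from the start, so about 6 − 2 = 4 weeks after the course ends.

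On either version the first outcome reading after the complete course is 4 to 6 weeks late.

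**3. What each planned contrast estimates**

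| Contrast | Sessions given | What it reflects |
|---|---|---|
| T1 − T0 | about 5 of 10 | response to about half the course |
| T6 − T0 | 10 of 10 | full-course effect less its decay, plus other change over time |
| End of course − T0 | 10 of 10 | not scheduled |

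**4. Illustration of what reading at half-course could cost.** All inputs except n and alpha are assumptions.
- n = 10 (section 6.2); two-sided alpha 0.05 (Data Analysis).
- Assumed: effect builds linearly to 0.8 SD at session 10, hence 0.8 × 5/10 = 0.4 SD at session 5.
- Within-subject correlation r assumed at 0.5, 0.7 and 0.8.
- SD of change = √(2(1 − r)); standardised change = effect / SD of change; non-centrality = standardised change × √10; 9 degrees of freedom.

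| r | SD of change | Standardised change at T1 | Power at T1 | Standardised change at course end | Power at course end |
|---|---|---|---|---|---|
| 0.5 | 1.000 | 0.40 | 0.21 | 0.80 | 0.62 |
| 0.7 | 0.775 | 0.52 | 0.31 | 1.03 | 0.83 |
| 0.8 | 0.632 | 0.63 | 0.43 | 1.26 | 0.94 |

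If the effect has already plateaued by session 5, the T1 and course-end columns coincide and nothing is lost in power. The planned schedule could not show that this had happened.

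**The case against.** **The full course is measured.** A reader might infer from the schedule that the before-and-after objective is never assessed after complete treatment, or that neither paired t-test addresses it. The protocol does not support that. T6 follows all 10 sessions and is tested against baseline, and the objective does not say that the second reading must be immediate or at peak effect. This stands. The gap is a missing reading at or soon after completion, not the absence of any full-course reading.

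**T1 may mean one week after the course.** The wording is loose. However, the Data Analysis paragraph sets one week of intervention against six weeks post-intervention, which favours mid-course. A site following the text would record then. If the other meaning was intended, the half-course argument falls and the wording needs correcting.

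**The power figures are not the protocol's.** This is correct. Effect size, correlation and linear build-up are all assumed. Section 2.1 describes EEG changes during and after a single session, which gives no support for linear accumulation. The study is exploratory and has no power target. The figures show only what could be lost, and the problem of interpretation does not rest on them.

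**An EEG straight after the last session may pick up acute after-effects.** Section 2.1 reports raised alpha and beta power during and after stimulation. A fixed interval would standardise this contribution without removing it.

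**The schedule is coherent for an exploratory study.** A mid-course reading plus a follow-up invalidates neither planned comparison. That limits the severity, but it does not supply the missing reading.

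**Conclusion.** The point holds in this form: as worded, no EEG, FTND or MNWS is taken at or soon after completion of the 10-session course. T1 comes at about 5 of 10 sessions, and T6, the only full-course reading, is 4 or 6 weeks delayed according to which section applies. The trial can estimate a half-course response and a delayed full-course contrast. It cannot estimate the effect at the end of the course, and it cannot separate fading from a second week without added effect.

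This rests on the mid-course reading of T1, which the text favours but does not settle. The timeline needs no other assumption. The size of any power loss does: it runs from none, if there is a plateau by session 5, to the gaps tabulated above under linear build-up. Severity: should-fix.

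**What to change.** Move the T1 EEG, FTND and MNWS to the end of week two, at one fixed interval after the last session for every subject. Align the three paragraphs of section 5.2 that name the time points: EEG Assessments, Assessment of Nicotine Dependence and Withdrawal symptoms, and Data Analysis. If the sponsor meant T1 as one week after the course, reword it to say so. Separately, reconcile T6 between section 5.2 and sections 5.6 and 5.7, because this determines how delayed the follow-up reading is.

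**Cost.** This is an amendment to wording. The number of recordings stays at three and the stimulation schedule is untouched. The mid-course reading is lost, and the protocol states no purpose for it; a fourth recording would keep it at the price of one more assessment. EEG must be feasible at or shortly after the last treatment visit. Subjects already attend that visit, but the protocol does not establish that a recording can be made there.
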